4.3.2 AEs and SAEs

AEs will be summarized using MedDRA System Organ Class and preferred terms. Tables will show by treatment group the number and percentage of participants experiencing an AE within a System Organ Class or within preferred term category by severity or by relationship to study product. For the calculations in these tables, a participant with multiple AEs within a category will be counted once under the maximum severity or the strongest recorded causal relationship to study product. Formal statistical testing comparing groups is not planned since interpretation of differences must rely heavily upon clinical judgment.

A listing of SAEs reported to the DAIDS Regulatory Support Center (RSC) Safety Office will provide details of the events including severity, relationship to study product, time between onset and last vaccination, and number of vaccinations received. A separate listing will do the same for AEs of special interest (AESI). AESI for this protocol include but are not limited to potential immune-mediated disorders; a sample list of AESI is provided in Appendix H of the Protocol. These listings will be submitted to the FDA in all annual reports and clinical trial reports.

4.3.3 Local laboratory values

Boxplots of local laboratory values will be generated for baseline values and for values measured during the course of the study by treatment group and visit. Each boxplot will show the first quartile, the median, and the third quartile. Outliers (values outside the boxplot) will also be plotted. If appropriate, horizontal lines representing boundaries for abnormal values will be plotted.

For each local laboratory measure, summary statistics will be presented by treatment group and timepoint, as well as changes from baseline for postenrollment values. In addition, the number (percentage) of participants with local laboratory values recorded as meeting Grade 1 AE criteria or above as specified in the DAIDS AE Grading Table will be tabulated by treatment group for each postvaccination timepoint. Reportable clinical laboratory abnormalities without an associated clinical diagnosis will also be included in the tabulation of AEs described above.

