1.2. Study Objectives and Endpoints

Primary objectives and endpoints

Primary objective 1

- To evaluate the safety and tolerability of ALVAC-HIV and bivalent gp120 protein/MF59 or bivalent gp120 protein/AS01_B.

Primary endpoints 1

- Severe local and systemic reactogenicity signs and symptoms (pain, tenderness, erythema, induration, fever, malaise/fatigue, myalgia, headache, nausea, vomiting, chills, arthralgia) up to 7 days after each vaccine dose
- AEs by body system, Medical Dictionary for Regulatory Activities (MedDRA) preferred term, severity, and assessed relationship to study products up to 30 days after each vaccine dose
- SAEs, AESIs, and new chronic conditions (requiring medical intervention for ≥ 30 days) throughout the study
- Laboratory measures: white blood cells (WBC), neutrophils, lymphocytes, hemoglobin, platelets, alanine aminotransferase (ALT), aspartate aminotransferase (AST), alkaline phosphate (ALP), and creatinine at baseline and following vaccinations
- AEs leading to early participant withdrawal or early discontinuation of study products administration throughout the study.

Primary objective 2

- To compare HIV-specific CD4+ T-cell response rates at the month 6.5 timepoint (2 weeks after the fourth vaccination) of ALVAC-HIV and bivalent gp120 protein/MF59 to each of the bivalent gp120 protein/AS01_B vaccine regimens.

Primary endpoint 2

- HIV-specific CD4+ T-cell response rates as assessed by flow cytometry.

Primary objective 3

- To compare HIV-specific Env-gp120 binding antibody response magnitudes at the month 12 timepoint (6 months after the fourth vaccination) of ALVAC-HIV and bivalent gp120 protein/MF59 to each of the bivalent gp120 protein/AS01_B vaccine regimens.

Primary endpoint 3

- HIV-specific Env-gp120 binding antibody response magnitude as assessed by multiplex assay.

Secondary objectives and endpoints

Secondary objective 1

- To further evaluate the systemic immune responses and the durability of immunogenicity of each vaccine regimen at the month 6.5 and month 12 timepoints.

Secondary endpoint 1

- HIV-specific total IgG binding antibody response breadth and magnitude as assessed by multiplex assay.
- Anti –V1/V2 scaffold IgG binding antibody responses as assessed by multiplex assay.
- HIV-specific CD4+ and CD8+ T-cell responses as assessed by flow cytometry.
- Additional immunogenicity assays may be performed on blood samples based on the HVTN Laboratory Assay Algorithm

Exploratory objectives

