5 SAFETY TABLES AND FIGURES

5.1 List of Tables (see mock tables in Appendix A)

SMB reports and Safety FSRs include the following tables.

- Enrollment Report
- Demographics and Study Product Administration Frequencies
- Overall Protocol Status
- Maximum Local Reactogenicity Summary
- Maximum Systemic Reactogenicity Summary
- Adverse Experiences by Body System and Severity – By Decreasing Frequency
- Adverse Experiences by Preferred Term and Severity – By Decreasing Frequency – Includes Severe, Potentially Life-threatening or Fatal Events Only
- Adverse Experiences by Preferred Term and Severity – By Decreasing Frequency – Includes Events of All Severities
- Adverse Experiences by Preferred Term and Relationship to Study Product – By Decreasing Frequency – Includes Related Events Only
- Adverse Experiences by Preferred Term and Relationship to Study Product – By Decreasing Frequency – Includes Events of Any Relationship
- Expedited Adverse Events (EAEs) Reported to the Regulatory Support Center (RSC)
- Pregnancy Listing
- Adverse Events of Special Interest

Safety FSRs include the following additional tables.

- Social Impact Summary
- Local Lab Value Summary Statistics
- Local Laboratory Values Meeting Grade 1 AE Criteria or Above

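### The graded laboratory table counts Grade 1 or higher values after vaccination without reference to the participant's own baseline grade, so abnormalities present at entry are mixed with new or worsened ones

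*SAP*

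**What the plan says.** SAP section 1.2 lists nine laboratory measures, from white cells to creatinine, under the first primary (safety) endpoint, to be assessed "at baseline and following vaccinations".

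Section 4.3.3 plans these displays:

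- Plots: "Boxplots of local laboratory values will be generated for baseline values and for values measured during the course of the study", by group and visit. Outliers are drawn, and limits for abnormal values are added where appropriate. Section 5.3 lists the same plots.
- Summary statistics by group and timepoint, "as well as changes from baseline for postenrollment values".
- A graded count: "the number (percentage) of participants with local laboratory values recorded as meeting Grade 1 AE criteria or above", using the DAIDS grading table, which "will be tabulated by treatment group for each postvaccination timepoint".
- A link to the AE tables: "Reportable clinical laboratory abnormalities without an associated clinical diagnosis will also be included in the tabulation of AEs described above".

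Section 5.1 names the output of the graded count "Local Laboratory Values Meeting Grade 1 AE Criteria or Above". Neither section 4.3.3 nor the output lists in sections 5.1 to 5.3 mention a new-or-worsened rule, a baseline row for the graded count, or a shift table.

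**The concern.** The graded count is the only laboratory summary in section 4.3.3 that is expressed in clinical grades, so it is where a reader will look for signs of toxicity. As the rule is written, a participant whose haemoglobin or neutrophil count is Grade 1 at entry and never moves appears as abnormal at every timepoint after vaccination. The percentage shown is then the sum of two things: abnormality carried over from entry, and abnormality that arose or worsened after vaccination. Only the second bears on the safety of the regimens.

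Two consequences follow. The level of abnormality in every group may be overstated. And with groups of 50, a chance difference in entry abnormalities passes straight into the comparison between regimens. The placebo group has 10 participants and is a weak reference for telling the two components apart. Section 3 of the SAP itself warns that unrelated events may by chance fall more often in one arm. Its remedy, the clinician's judgement of relationship to product, is not part of the graded count as section 4.3.3 describes it.

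**Working it through.** **Reading.** The SAP gives no figure on this point, so there is none to reproduce. The planned displays can be set against the question of how many participants in each group had a new or worsened graded value.

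| Display | Uses baseline? | In grades? | Shows new or worsened within participant? |
|---|---|---|---|
| Boxplots (4.3.3, 5.3) | Yes, by group | No; limit lines only where appropriate | No |
| Change from baseline (4.3.3) | Yes, within participant | No, continuous values | No; averaged over the group |
| Graded count (4.3.3, 5.1) | Not in the stated rule | Yes | No |
| AE tables (4.3.2) | Not stated | By severity, for reportable abnormalities only | Not stated; the SAP does not define reportable |

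No planned display described in the SAP text answers the question.

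**Illustration of size.** One analyte at one timepoint.

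Input from the SAP: 50 participants per vaccine group (Table 3-1 in section 1.1).

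Assumed inputs, because the SAP gives none of them:

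- entry prevalence of Grade 1 or higher, b = 5%, 10%, 20%
- share of entry abnormalities still present after vaccination, s = 80%
- new onset among those normal at entry, i = 4%

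Formulas: carried over q = b·s; new = (1 − b)·i; displayed = q + new. For b = 10%: q = 0.10 × 0.80 = 0.080; new = 0.90 × 0.04 = 0.036; displayed = 0.116.

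For chance imbalance between two groups with no vaccine effect, only the carried-over part reaches the table. The standard deviation of the difference is therefore √(2q(1 − q)/50), and the 95% range is ±1.96 times that. For b = 10%: √(2 × 0.08 × 0.92/50) = 0.0543, and 1.96 × 0.0543 = 0.106.

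| Entry prevalence b | Carried over q | New | Displayed | SD of difference | 95% range of difference |
|---|---|---|---|---|---|
| 5% | 4.0% | 3.8% | 7.8% | 0.039 | about ±8 points |
| 10% | 8.0% | 3.6% | 11.6% | 0.054 | about ±11 points |
| 20% | 16.0% | 3.2% | 19.2% | 0.073 | about ±14 points |

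In participants per group of 50, b = 10% means 50 × 0.08 = 4.0 carried over and 50 × 0.036 = 1.8 new. For two independent binomial counts with n = 50 and q = 0.08, the exact probability of a gap of 5 or more participants is about 0.095.

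In the placebo group of 10, the chance of at least one carried-over abnormality at q = 0.08 is 1 − 0.92^10 = 0.57. The group may easily show none, or one, for reasons unrelated to any product.

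**Sensitivity.** Over a wider assumed range (b from 2% to 20%, s from 50% to 100%, i from 2% to 5%), carried-over participants run from 50 × 0.02 × 0.5 = 0.5 to 50 × 0.20 × 1.0 = 10 per group of 50. Their share of the displayed count runs from 17% to 93%. If eligibility excludes Grade 1 values for an analyte, b = 0 and the effect is nil.

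**The case against.** The strongest case against runs as follows.

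- **The plan does not ignore baseline.** A reader might infer that it does. It plans baseline boxplots by group with outliers drawn, so a marked imbalance at entry could be seen, and it summarises change from baseline. This stands as a limit on the concern. These displays describe continuous values by group, however, and do not separate carried-over grades from new ones.
- **The table layout is not visible.** Section 5.1 points to mock tables in Appendix A, which are not shown. A reader might infer that all grades are pooled, so that a move from Grade 1 to Grade 3 is hidden. The documents do not support that: the wording sets Grade 1 as the lower limit for inclusion and does not say that grades share one row. Splitting by grade would reveal more severe values but would still not separate pre-existing from new ones. A baseline column is also possible, although the text limits the count to timepoints after vaccination.
- **Important worsening has another route.** Reportable abnormalities enter the AE tables, with severity and relationship, and section 5.2 lists severe or worse events individually for the SMB. This stands. The threshold for reporting may be in the protocol, so how much this route catches cannot be judged here.
- **Nothing is tested.** The count is descriptive, no decision rule rests on it, and randomisation balances entry grades in expectation. This stands and lowers the weight of the point. With no test, though, readers judge the percentages directly, so what is counted still matters.
- **The sizes are assumed.** The trial enrols healthy adults, and entry limits are not given in the SAP. This stands in full.

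**Conclusion.** The point holds as a reporting weakness in a primary safety endpoint. The stated rule counts any value of Grade 1 or higher after vaccination, and no other planned display shows how many graded abnormalities were new or worsened within participants.

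A reader might go further and conclude that the table presents entry abnormalities as vaccine toxicity. The SAP does not support that. It labels the table as values meeting grading criteria and does not call them treatment-emergent.

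The size is unknown, because the SAP gives no entry prevalence. The figures above rest wholly on assumed prevalence, persistence and new onset, and show only that the carried-over part can equal or exceed the new part under plausible inputs. They use the 50 per group of Table 3-1. Section 1.5 speaks of 100 per vaccine group; at that size the 95% ranges would shrink by √2, to about ±5.4, ±7.5 and ±10.2 points (7.68, 10.63 and 14.37 each divided by 1.414), while the displayed and new percentages would not change.

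Priority is low to moderate. Confidence is moderate, because the Appendix A mock tables are not shown and may already split grades.

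**What to change.** In section 4.3.3, and in the matching table of section 5.1:

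1. Count participants whose grade after vaccination is higher than their own baseline grade, by grade reached, per analyte, group and timepoint.
2. Add a shift table of baseline grade against worst grade after vaccination, per analyte and group.
3. Keep the present all-values table as a supplement.

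The baseline values are already part of the endpoint, so no new samples or visits are needed. The cost is SAP wording, one reprogrammed table and one added table. The headline abnormality percentages will be lower wherever entry abnormalities persist, and unchanged for analytes with none at entry.

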4.3.4 Reasons for vaccination discontinuation and early study termination

The number and percentage of participants who discontinue vaccination and who terminate the study early will be tabulated by reason and treatment group.

4.4 Immunogenicity Analysis

4.4.1 General approach

For the statistical analysis of immunogenicity endpoints, data from enrolled participants will be used according to the initial randomization assignment regardless of how many injections they received. Additional analyses may be performed, limited to participants who received all scheduled injections per protocol. Assay results that are unreliable, from specimens collected outside of the visit window, or from HIV-infected participants after infection are excluded. Since the exact date of HIV infection is unknown, any assay data from blood draws 4 weeks prior to an infected participant's last seronegative sample and thereafter may be excluded. If an HIV-infected participant does not have a seronegative sample after enrollment, then all data from that participant may be excluded from the analysis.

Response rates will be analyzed by tabulating the frequency of positive response for each endpoint and treatment group at each timepoint for which an assessment is performed. For CD4+

and CD8+ T-cell response, response rates to the individual peptide pools will also be calculated. Crude response rates will be presented with their corresponding 95% confidence interval estimate calculated using the score test method [1]. For the primary endpoints of CD4+ T-cell response rates for TV1 and 1086, differences between groups will be tested with a 2-sided Barnard's exact test at an alpha level of 0.05. For secondary and exploratory assay endpoints, response rates and 95% confidence intervals will be calculated if appropriate for the endpoint. No adjustment will be made to the vaccine group estimates for the false positive rates in the placebo group.

The primary endpoint of anti-gp120 binding antibody response magnitude, and likely some of the secondary assays, will have quantitative assay data. Other quantitative measures include binding antibody magnitude from the multiplex assay, neutralizing antibody titers, area under the magnitude-breadth curve [AUC-MB] for the neutralizing antibody assay, and percentage of positive cells from the ICS assay. Quantitative data will be displayed as graphical and tabular summaries of the distributions by antigen, treatment group, and timepoint. For the primary and secondary immunogenicity endpoints, box plots and plots of estimated reverse cumulative distribution curves will be presented by group. For the primary endpoint, differences between groups will be tested with a nonparametric Wilcoxon rank sum test if the data are not normally distributed or with a 2-sample t-test if the data appear to be normally distributed, at an alpha level of 0.05.

Formal statistical comparisons between groups for secondary and exploratory immunogenicity endpoints are not objectives of the trial, although these are likely to be made to better understand the effect of each vaccine regimen. For comparisons in which the response rate for 1 of the groups is low (eg, $\leq 20\%$ for the class), statistical testing will use Barnard's exact test comparing the 2 response rates as most of the continuous data readouts would be left censored at the lower limit of detection. For comparisons in which the response rates for both groups are high (eg, $\geq 75\%$), the difference between groups will be tested using the continuous readouts with a nonparametric Wilcoxon rank sum test if the data are not normally distributed and with a 2-sample t-test if the data appear to be normally distributed.

Some immunologic assays have underlying continuous or count-type readout that are dichotomized into responder/nonresponder categories. If treatment group differences for these assays are best summarized by a mixture model, then either Lachenbruch's test statistic [2] will be used to evaluate the composite null hypothesis of equal response rates in the 2 groups and equal response distributions among responders in the 2 such groups. For estimation, differences in response rates between groups will be estimated using the methods described above, and in the subgroup of positive responders, differences in location parameters between groups will be estimated using the methods described above.

4.4.2 Missing data considerations

Based upon previous HVTN trials, missing 15% of immunogenicity results for a specific assay is common due to study participants terminating from the study early, problems in shipping specimens, or low cell viability of processed PBMCs. To achieve unbiased statistical estimation and inferences with standard methods applied in a complete-case manner (only including participants with observed data in the analysis), missing data need to be missing completely at random (MCAR). MCAR assumes that the probability of an observation being missing does not depend on any participant characteristics (observed or unobserved). When missing data are minimal (specifically, if no more than 20% of participants are missing values), then standard complete-case methods will be used, because violations of the MCAR assumption will have little impact on the estimates.

If a substantial amount of immunogenicity data are missing (at least 1 value missing from more than 20% of participants), then using the methods that require the MCAR assumption may give

misleading results. In this situation, analyses of the immunogenicity endpoints at a specific timepoint will be performed using parametric generalized linear models fit by maximum likelihood. These methods provide unbiased estimation and inferences under the parametric modeling assumptions and the assumption that the missing data are missing at random (MAR). MAR assumes that the probability of an observation being missing may depend upon the observed responses and upon observed covariates, but not upon any unobserved factors. Generalized linear models for response rates will use a binomial error distribution and for quantitative endpoints, a normal error distribution. For assessing repeated immunogenicity measurement, linear mixed effects models will be used. If the immunological outcomes are left- and/or right-censored, then the linear mixed effects models of Hughes [3] will be used, because they accommodate the censoring. In addition, secondary analyses of repeated immunogenicity measurements may be done using weighted GEE [4] methods, which are valid under MAR. All of the models described above will include as covariates all available baseline predictors of the missing outcomes.

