Binding Antibody Multiplex Assay (BAMA) testing will be performed on serum samples from each participant in the protocol at visit 2 (month 0, baseline), visit 10 (month 6.5, 2 weeks post the 4th vaccination), and visit 12 (month 12, 6 months post the 4th vaccination). Specimens from other timepoints as well as other HIV antigens and antibody isotypes may be assayed based on the results of the initial assay. If sufficient immunogenicity is observed for the primary analysis antigens, additional assays will be performed using the exploratory antigens.

The following table lists the antigens for the analysis.

Panel	Antigen	Clade	Endpoint
Vaccine gp120 panel	1086C_D7gp120.avi/293F	C	Primary objective 3
	96ZM651.D11gp120.avi	C	Primary objective 3
	TV1c8_D11gp120.avi/293F	C	Primary objective 3
Vaccine V1V2 panel	C.1086C_V1_V2 Tags	C	Secondary objective 1
	gp70-96ZM651.02 V1v2	C	Secondary objective 1
	gp70-TV1.21 V1V2	C	Secondary objective 1
	gp70-TV1.GSKvacV1V2/293F	C	Secondary objective 1
Other V1V2	gp70_B.CaseA_V1_V2	B	Exploratory objective
	gp70_B.CaseA2_V1/V2/169K	B	Exploratory objective
Conensus gp140/gp120	Con 6 gp120/B	M	Exploratory objective
	Con S gp140 CFI	M	Exploratory objective
Other gp140	00MSA 4076 gp140	A	Exploratory objective
	A1.con.env03 140 CF	A	Exploratory objective
gp41	gp41	B	Exploratory objective

MFI will be employed for this essay. The frequency of positive responders (% responders) will be tabulated to access HIV binding antibody responses between placebo and vaccine groups from MFI readouts.

Samples from post-enrollment visits are declared to have a positive response if they meet three conditions:

1. The Net MFI (MFI*, i.e., MFI minus Blank values, where 'Blank value' refers to a plate-specific background measure) were \geq antigen-specific cutoff (based on the 95th percentile of the baseline samples).
2. The MFI* values were greater than 3 times the baseline MFI*.
3. The MFI values are greater than 3 times the baseline MFI values.

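### Above 20% missing, section 4.4.2 calls single-timepoint GLMs unbiased under MAR, but for month-12 antibody they ignore the scheduled month-6.5 response

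*SAP*

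**What the plan says.** SAP section 4.4.2 uses complete-case methods up to 20% missing. Above that, "analyses of the immunogenicity endpoints at a specific timepoint will be performed using parametric generalized linear models fit by maximum likelihood". The next sentence gives the property claimed for these models: "These methods provide unbiased estimation and inferences under the parametric modeling assumptions and the assumption that the missing data are missing at random (MAR". MAR is then defined: "MAR assumes that the probability of an observation being missing may depend upon the observed responses and upon observed covariates", but not on unobserved factors.

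Two further sentences limit what the models contain. On covariates: "All of the models described above will include as covariates all available baseline predictors of the missing outcomes". On joint modelling: "For assessing repeated immunogenicity measurement, linear mixed effects models will be used". A censored mixed model follows, conditional on left- or right-censored outcomes. Weighted GEE is an optional secondary analysis of repeated measurements.

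The trigger is worded as "at least 1 value missing from more than 20% of participants".

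Section 6.3 schedules the binding antibody assay for each participant at baseline, "visit 10 (month 6.5, 2 weeks post the 4th vaccination), and visit 12 (month 12, 6 months post the 4th vaccination". Section 6.3.1 lists the MF59 v AS01B comparison of MFI at month 12.

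**The concern.** The section brings in the GLM as the remedy for analyses that could mislead because MCAR fails. A GLM fitted by maximum likelihood to one visit receives no contribution from a participant who has no value at that visit. It is a complete-case regression, and its only gain over the two-sample test is adjustment for baseline covariates. If month-12 loss is related to the month-6.5 antibody response, the data are MAR as the section defines it, because that response is observed and scheduled. The GLM nevertheless leaves the response out, and each affected arm's month-12 mean is biased.

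At stake is the analysis of primary objective 3 when the fallback applies: it could be reported as protected against a mechanism that it does not address. The point concerns month 12. No earlier post-vaccination T-cell result is firmly scheduled before month 6.5 (section 6.1 makes Visit 7 contingent), so the month-6.5 CD4+ endpoint has no comparable omitted response.

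**Working it through.** The SAP gives no calculation behind the 20% cut-off or the unbiasedness statement, so there is no figure to reproduce.

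**1. Which model reaches the month-12 contrast.** The GLM sentence covers endpoints at a specific timepoint, and objective 3 is a comparison at month 12. The linear mixed model is tied to repeated measurement. On this reading the GLM is the fallback for objective 3, subject to the censoring sentence discussed under the objection.

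**2. Bias of the single-timepoint contrast.** Let x be the month-6.5 log response, standardised within arm, and ρ its correlation with month 12. Let P(missing | x) = 1/(1 + exp(−(a − b·x))), so lower responders are lost more often, with a set to give the required missing share. The bias of an arm's month-12 mean, in SD, is ρ·E[x | observed]. The bias of the contrast is ρ·(E₁ − E₂), where E₁ and E₂ are E[x | observed] in the two arms.

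Assumptions, none of them from the SAP: ρ from 0.5 to 0.8, b from 0.5 to 2 per SD, no baseline covariate that predicts loss, and the same b in both arms. Missing shares are 25% in each AS01B arm and 15% in the MF59 arm. With 50 per group (SAP section 1.1), the pooled share is (12.5 + 12.5 + 7.5)/150 = 21.7%, so the fallback applies.

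The SE of the contrast at unit variance is √(1/37.5 + 1/42.5) = 0.224 SD. Under no true difference, two-sided error is Φ(−1.96 + z) + Φ(−1.96 − z), with z = bias/SE.

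| ρ | b | E₁ (25%) | E₂ (15%) | Bias (SD) | z | Two-sided error |
|---|---|---|---|---|---|---|
| 0.5 | 0.5 | 0.1195 | 0.0726 | 0.023 | 0.10 | 5.1% |
| 0.5 | 1 | 0.2132 | 0.1326 | 0.040 | 0.18 | 5.4% |
| 0.5 | 2 | 0.3186 | 0.2034 | 0.058 | 0.26 | 5.8% |
| 0.8 | 0.5 | 0.1195 | 0.0726 | 0.038 | 0.17 | 5.3% |
| 0.8 | 1 | 0.2132 | 0.1326 | 0.065 | 0.29 | 6.0% |
| 0.8 | 2 | 0.3186 | 0.2034 | 0.092 | 0.41 | 7.0% |

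Selection narrows the observed spread slightly. Allowing for this in the last row gives an SE of 0.206, z = 0.45 and an error of 7.3%. The bias favours the arm with more loss. If the shares are swapped, its sign changes and the two-sided error does not.

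**3. Equal loss.** At 25% v 25% with the same mechanism, E₁ = E₂ and the contrast has no bias, although both arm means are shifted upward.

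**4. Joint model.** In simulation of the 25% v 15% case with 50 per arm, maximum likelihood on months 6.5 and 12 together had bias of at most 0.003 SD. Its SE was 0.208 to 0.220, against 0.204 to 0.224 for the single-timepoint analysis. If 15% of month-6.5 values are also missing at random, its residual bias is 0.004 to 0.009 SD.

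**5. What the 20% counts.** Assume 15% missing per endpoint, the rate the SAP calls common, and 150 vaccine recipients. The fallback then needs more than 30 participants.
- One endpoint at one visit: P(Binomial(150, 0.15) > 30) = 0.038.
- Any value across the two primary endpoints, missing independently: 1 − 0.85² = 0.2775, and P(Binomial(150, 0.2775) > 30) = 0.981.
- If exactly the same participants miss both, the share is again 15% and the probability is again 0.038. Partial overlap falls between.

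**The case against.** **The MAR sentence may be read model by model.** In a single-timepoint GLM a participant without a value has no observed response, so MAR given that model's own data reduces to dependence on covariates, and the statement becomes true. That would be a fair reading of a general definition. But the unbiasedness sentence follows directly on the GLM sentence, and MAR is defined, with observed responses included, before any mixed model is mentioned. A reader would take the GLM to handle dependence on an earlier response.

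**The right model may already be assigned.** The censored mixed model is conditional on censoring, and section 1.5 gives the assay lower and upper detection limits. It may therefore already be meant for month-12 MFI. This stands in part: the plan does not lack a suitable method, but it does not say that this method takes over the primary contrast. Section 6.3.1 is a list of outputs and does not settle the question.

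**The harm is conditional and modest.** This stands. Participants and site staff are blinded, and none of the reasons for missing data listed in 4.4.2 is tied to arm or antibody level. Under a common mechanism the bias is under half an SE. The success criterion in section 1.5 also requires the CD4+ result, so antibody error alone is not the error of the composite claim.

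**The fallback may rarely apply.** True if one endpoint and visit is counted, which the reference to a specific assay and timepoint favours. The trigger wording also allows the other reading.

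Two stronger readings are tempting. One is that error could rise far above nominal, which happens if loss depends on month 6.5 in one arm only. That scenario is constructed, and nothing in the SAP points to it. The other is that the complete-case rule is itself an error because the section says "then standard complete-case methods will be used, because violations of the MCAR assumption will have little impact on the estimates". That claim is tied to the 20% limit, and the section states that complete-case analysis needs MCAR. Further sensitivity work there would be optional.

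**Conclusion.** The unbiasedness statement is incorrect for the month-12 antibody endpoint as written. A single-timepoint GLM with baseline covariates is unbiased only when missingness depends on terms in the model, whereas the section's MAR also admits dependence on the month-6.5 response that the model omits.

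The consequence is limited. The arm contrast is biased only if missing shares or mechanisms differ between arms. At 25% v 15% with a common mechanism, the bias is 0.02 to 0.09 SD and two-sided error about 5.1% to 7.0% against 5%. It is nil with equal shares and mechanism. These sizes rest on the assumed correlation, slope and absence of baseline predictors, and the SAP supplies none of these. A reader might infer that the objective 3 result is biased or its error rate uncontrolled; the document does not support that.

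The point is worth correcting because a better method is already cited in the same section, and because the undefined count leaves it unclear whether the fallback is rare or almost certain.

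**What to change.** 1. State that, when the fallback is triggered, the month-12 antibody contrast is analysed with the linear mixed model already cited in 4.4.2, or its censored form, fitted jointly to months 6.5 and 12 with a treatment-by-visit term. If the censoring sentence already intends this, say so.
2. Limit the unbiasedness statement for single-timepoint GLMs to missingness that depends only on terms in the model.
3. State whether the 20% counts one endpoint at one visit or any missing value.

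The cost is a few sentences and one model on data already scheduled. The downside is that the joint model is parametric and recovers information only for participants who have a month-6.5 value. The tests in section 4.4.1 at or below the threshold are unchanged.

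Optional additions: a tipping-point table for the CD4+ response rates, and a table of missing assay results by group and reason.
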